Subjects who do not tolerate a dose of 3 mg/kg qw or 1 mg/kg qw may receive a dose reduction to 1 mg/kg qw or 0.35 mg/kg qw, respectively, at the discretion of the Investigator in consultation with the Sponsor and, where appropriate, the SC. If a subject cannot tolerate a dose of 0.35 mg/kg qw, despite measures taken to manage any IARs, the subject will be discontinued from the study.

Subjects who are on treatment for at least 96 weeks and have been on a stable dose for at least 24 weeks, may transition to an every other week dosing schedule at the same dose they received on the weekly dosing schedule. If the subject meets the criteria for dose escalation while on the every other week dosing schedule they will either revert back to weekly dosing or if on 1 mg/kg qow can increase to 3 mg/kg qow dosing.

Given the severity and life threatening nature of rapidly progressive LAL Deficiency, it is likely that these subjects will be hospitalized during the first several weeks on study. For the subjects Page **26** of **76**

who are stable enough to be treated on an outpatient basis, safety follow-up assessments for AEs will be conducted by telephone 24 hours following the first 2 infusions of 0.35 mg/kg qw, 1 mg/kg qw, as well as 3 mg/kg qw, if needed. Additional details about the SC review process can be found in Section 7.6. Refer to Appendix A for the full Schedule of Assessments.

Subjects who appear to have an acute illness (e.g., upper respiratory infection or febrile illness) should have their scheduled infusions postponed by up to 2 days (5 days if subject is on a qow infusion schedule) to allow for resolution. If the illness persists for longer than 2 days (5 days if subject is on a qow infusion schedule), the infusion schedule should reset to the next scheduled infusion after the subject's recovery. The Investigator may conduct an unscheduled visit at any time during the study at his/her discretion. Assessments performed at this visit should be symptom directed. Safety laboratory testing may be performed if the Investigator considers it necessary. Repeat laboratory testing may be needed based on results from the unscheduled laboratory testing. If the subject is discontinued from study treatment at a scheduled visit or at an unscheduled visit, the subject should return no earlier than 7 days after the last dose of IMP for an End of Study assessment.

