8.8.1 Adverse Events

All reported AEs will be listed from the start of dosing with sebelipase alfa to the end of participation in this study. Separate listings of SAEs and IARs will also be provided. The numbers and percentages of subjects experiencing any AE, any SAE, any IAR, any related AE, any related SAE, and discontinuations due to an AE will be tabulated.

The frequency of treatment-emergent AEs, SAEs, and IARs by system organ class SOC and preferred term (coded using Medical Dictionary for Regulatory Activities [MedDRA[®]] version 14 or higher) will be tabulated. Frequencies will also be presented by the classifications of severity and causality. In addition, frequency of AEs, SAEs, and IARs will be presented for time periods spanning the entire course of treatment with sebelipase alfa: from the start of dosing with sebelipase alfa in this study to 3 months after the first dose, >3 to 6 months, >6 to 12 months, >12 to 18 months, >18 to 24 months and >24 months. As appropriate, additional listings, summary tables and graphics will be generated to evaluate IAR frequency and severity over time. A listing of subjects who withdraw from the study due to AEs will be presented, and the incidence of AEs leading to study discontinuation will be summarized.

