 Moderate Reaction Hyperemia (flushing) Chest discomfort Itching and/or raised urticarial rash Severe headache Gastro intestinal symptoms, vomiting, diarrhoea, abdominal cramping. 	 Stop Infusion Give antihistamine IV and consider IV steroids Give any prescribed inhaler treatment if appropriate If the event has resolves, the infusion may continue at reduced rate of 50% of the original for a minimum of 30 minutes before infusion is increased to 75% of original rate. If patient tolerates infusion at 75% of the original rate for at least 30 minutes the original rate for at least 30 minutes the original rate may be restored for the remainder of the infusion. Pre-treat with oral antihistamine and antipyretic prior to next infusion Collect serum sample for tryptase 1-3 hours after the IAR onset and another serum sample for tryptase and ADA during the next study visit (≥ 4 days after the IAR) prior to the infusion. Skin testing may be considered.

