2.1 Summary of Amendments

The following updates have been made to the planned analysis:

- Urinalysis and ADA assessments will only be presented in the listings. Summaries will not be presented.
- For specified lab parameters, change from baseline and percent change from baseline will not displayed in spaghetti plots.
- The per protocol analysis set will not be used to summarize results.
- Adverse event will be presented for time periods spanning the entire treatment period. The periods that will be used are 0 to 12 Months, >12 to 24 Months, >24 to 36 Months, >36 to 48 Months, and >48 Months
- Denver II scores will only be presented in a listing.

STATISTICAL ANALYSIS PLAN

An Open Label, Multicenter, Dose Escalation Study To Evaluate The Safety, Tolerability, Efficacy, Pharmacokinetics, and Pharmacodynamics of SBC-102 in Children with Growth Failure Due to Lysosomal Acid Lipase Deficiency

Protocol LAL-CL03

Protocol Number: LAL-CL03

Protocol Version and Date: Amendment 10: 24 January 2014

Amendment 9: 19 March 2013 Amendment 8: 05 February 2013 Amendment 7: 23 October 2012 Amendment 6: 05 April 2012 Amendment 5: 20 September 2011 Amendment 4: 02 June 2011 Amendment 3: 20 May 2011 Amendment 2: 19 April 2011 Amendment 1: 09 February 2011

Original: 10 January 2011

Name of Test Drug: SBC-102 (sebelipase alfa)

Methodology: Open Label, Multicenter, Dose Escalation

Sponsor: Synageva BioPharma Corp.

[name]

Tel: PPD Fax: PPD

Sponsor Representative:

PPD PPD

Synageva BioPharma Corp.

Analysis Plan Date: 07 March 2014

Analysis Plan Version: Final Version 1.1

Confidentiality Statement

The information contained herein is confidential and the proprietary property of Synageva BioPharma Corp. and any unauthorized use or disclosure of such information without the prior written authorization of Synageva BioPharma Corp. is expressly prohibited.

APPROVAL SIGNATURE PAGE

Protocol Title:

An Open Label, Multicenter, Dose Escalation Study To

Evaluate The Safety, Tolerability, Efficacy,

Pharmacokinetics, and Pharmacodynamics of SBC-102 in Children with Growth Failure Due to Lysosomal Acid

Lipase Deficiency.

Sponsor:

Synageva BioPharma Corp.

[name]

Protocol Number:

LAL-CL03

Document Date / Version:

07 March 2014 / Final Version 1.1

PPD

Veristat, Inc. Author:

PPD

Signature:

Veristat, Inc.

[name] ate: 07 Mar 2014

Sponsor Approval

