- If the start date is completely missing, an AE will not be excluded from treatmentemergent AEs unless the stop date/time is before the start of first treatment.

An Overall AE summary table will be presented and will include the number of subjects with:

- All treatment-emergent AEs
- IRRs
- SAEs
- Treatment-emergent AEs related to SBC-102
- Treatment-emergent AEs leading to discontinuation from the study

Summaries of number of events and incidence rates (frequencies and percentages of subjects) of AEs by MedDRA SOC and Preferred Term will be prepared. Such summaries will also be displayed for all AEs by intensity and by relationship to study drug.

Each subject will be counted only once within each level of the summary. If a subject experiences more than one AE within a level, only the AE with the strongest relationship or the maximum intensity, as appropriate, will be included in the summaries of relationship and intensity.

No inferential statistical tests will be performed.

In addition, frequency of AEs, SAEs, and IRRs will be presented for time periods spanning the entire course of treatment with SBC-102: from the start of dosing with SBC-102 in this study to 3 months after the first dose, >3 to 6 months, >6 to 12 months, >12 to 18 months, >18 to 24 months and >24 months.

All AEs will be listed. Separate listings of SAEs, IRRs, AEs leading to study discontinuation, and AEs leading to discontinuation of SBC-102 will also be provided.

As appropriate, a summary of numbers of events and incidence rates (frequencies and percentages or subjects) of IRRs, and AEs leading to withdrawal from the study by SOC and Preferred Term will be prepared for the FAS. No inferential statistical tests will be performed.

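### Infusion reactions are summarised by time window without infusions as the denominator, so any trend over time mixes risk per infusion with the number of infusions

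*SAP*

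**What the plan says.** The Protocol calls these events infusion-associated reactions (IARs) and makes them AEs of special interest (6.5). The SAP calls them infusion-related reactions (IRRs). Safety and tolerability is a secondary objective (Protocol 2.2).

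- **View over time.** SAP 10.1: "frequency of AEs, SAEs, and IRRs will be presented for time periods spanning the entire course of treatment with SBC-102". The windows listed there run "from the start of dosing with SBC-102 in this study to 3 months after the first dose, >3 to 6 months", then >6 to 12, >12 to 18, >18 to 24 and >24 months. The SAP's Summary of Amendments updates them to "0 to 12 Months, >12 to 24 Months, >24 to 36 Months, >36 to 48 Months, and >48 Months".
- **Metric.** SAP 10.1 plans "Summaries of number of events and incidence rates (frequencies and percentages of subjects) of AEs by MedDRA SOC and Preferred Term". By default, percentages use all subjects in the analysis population (SAP 7.1).
- **Infusions.** SAP 10.1.2 summarises the number of infusions. It does not say by window, and does not link them to reactions.
- **Dosing schedule.** Subjects on treatment for at least 96 weeks, with at least 24 weeks on a stable dose, "may transition to an every other week dosing schedule at the same dose they received on the weekly dosing schedule" (Protocol 3.1).
- **Pre-treatment.** After a moderate reaction, Appendix B says: "Pre-treat with oral antihistamine and antipyretic prior to next infusion". It has a similar entry for mild reactions. Appendix C names pre-treatment as an example of how dosing may resume after a Grade 3 or higher reaction.
- **Further outputs.** Where appropriate, "additional listings, summary tables and graphics will be generated to evaluate IAR frequency and severity over time" (Protocol 8.8.1). No metric is defined.

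**The concern.** An infusion reaction can occur only when there is an infusion, so the natural exposure unit is the infusion. The committed table over time has no such denominator, and infusions per window are not constant by design. The windows in SAP 10.1 differ in length and the last is open-ended. The optional move from weekly (qw) to every-other-week (qow) dosing halves the infusions per unit of time.

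A reader of the report will want to know whether reactions become more or less common with continued treatment. The planned table could suggest either answer with no change in risk per infusion. Pre-treatment adds a different problem: it is started because a child has reacted, so a falling rate could reflect the pre-treatment and not developing tolerance.

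**Working it through.** The documents give no reaction rate and no count of infusions per window, so there is no stated figure to reproduce. The check counts infusions per window and asks what a constant risk would look like in the planned table.

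**Inputs from the documents**
- One infusion every 7 days from Week 0 to Week 260 (Protocol 3.1, up to 5 years; Appendix A). The SAP body describes weekly dosing for up to 4 years.
- Earliest switch to qow: Week 96, which is 96 × 7 / 30.4375 = 22.1 months, using the SAP 7.2 month length.

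**Assumptions**
- Risk per infusion r is constant and infusions are independent. The documents give no value, so r = 1%, 2%, 5% and 10% were tried.
- The subject stays on treatment throughout. In the switch scenario, the switch is at Week 96.

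**Formulas**
- Expected reactions per subject = r × n, where n is the number of infusions in the window.
- Share of subjects with at least one reaction = 1 − (1 − r)^n.

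**Windows in SAP 10.1**

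| Months | 0–3 | >3–6 | >6–12 | >12–18 | >18–24 | >24 |
|---|---|---|---|---|---|---|
| n, qw throughout | 14 | 13 | 26 | 26 | 26 | 156 |
| n, qow from Week 96 | 14 | 13 | 26 | 26 | 22 | 78 |
| Share with any, r = 1%, qow | 13% | 12% | 23% | 23% | 20% | 54% |
| Share with any, r = 5%, qow | 51% | 49% | 74% | 74% | 68% | 98% |

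Constant risk gives an overall rise, with a small dip in >18–24 months (26 to 22 infusions).

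**Windows in the Summary of Amendments**

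| Months | 0–12 | >12–24 | >24–36 | >36–48 | >48 |
|---|---|---|---|---|---|
| n, qw throughout | 53 | 52 | 52 | 52 | 52 |
| n, qow from Week 96 | 53 | 48 | 26 | 26 | 26 |
| Share with any, r = 1%, qow | 41% | 38% | 23% | 23% | 23% |
| Share with any, r = 2%, qow | 66% | 62% | 41% | 41% | 41% |
| Share with any, r = 5%, qow | 93% | 92% | 74% | 74% | 74% |
| Share with any, r = 10%, qow | 99.6% | 99.4% | 93.5% | 93.5% | 93.5% |

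For example, 1 − 0.99^53 = 41.3% and 1 − 0.99^26 = 23.0%. Expected counts fall from 53r to 26r, which is 1 − 26/53 = 51% for any r. On weekly dosing throughout, the table is flat.

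**With infusions as denominator.** The rate is r × n / n = r in every window, under both window sets and both schedules. The exposure artefact disappears.

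**Pre-treatment.** Suppose, as an assumption, that risk is multiplied by f = 0.5 for all infusions after a subject's first reaction. The expected risk at infusion k is P·r + (1 − P)·r·f, where P = (1 − r)^(k − 1) is the chance of no earlier reaction. With r = 5% and weekly dosing, the rate per infusion in the six SAP 10.1 windows is 4.33%, 3.41%, 2.85%, 2.59%, 2.52% and 2.50%. The denominator does not remove this fall, because risk per infusion has really fallen.

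**The case against.** A reader might infer that the planned table will make reactions appear to decline. The documents do not support that. The windows in SAP 10.1 push the other way. A decline from exposure alone needs the annual windows and subjects who switch. Switching is optional and cannot act before 22.1 months.

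A reader might also infer that pre-treatment makes reactions fall while risk per infusion does not. If pre-treatment works, risk per infusion does fall and the table reports that correctly. The open question is what caused the fall. Appendix B is headed as recommendations, follows institutional standard of care and refers to the next infusion, so continued pre-treatment is itself an assumption.

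The strongest defence is that nothing is lost. SAP 10.1 lists IRRs separately and allows listings in place of tables when events are few. SAP 7.1 attaches the infusion's dose to each IRR, SAP 10.1.2 lists all dosing, and SAP 10.1.3 lists concomitant medication. With about 10 subjects, a careful reader could reconstruct the picture child by child. Protocol 8.8.1 leaves room for further outputs over time. No inferential tests on AEs are planned, and neither document claims that reactions fall with treatment.

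That defence stands as far as it goes: this is a reporting gap, with the data in hand. It does not remove the point. The Protocol 8.8.1 outputs are discretionary and name no metric, so the only committed summary over time is one that cannot separate risk from exposure.

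**Conclusion.** The point holds as a limited one. The by-window IRR summary cannot be read as a trend in risk per infusion. Under constant risk it rises overall with the SAP 10.1 windows. With the annual windows, expected counts fall by about half after about month 24 in subjects who switch at Week 96. The share of those subjects with any reaction falls from 41% to 23% at an assumed 1% risk, and from 93% to 74% at 5%.

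The direction under each window set does not depend on the assumed risk, but the percentages do. The size also depends on how many children switch and when. The figures describe subjects who remain on treatment; deaths and withdrawals are not modelled. Pre-treatment is a separate confounder of any claim that tolerance develops, and the documents give nothing from which to size its effect.

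**What to change.** In SAP 10.1, add to the by-window IRR table:

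1. The number of infusions given in the window.
2. The number and percentage of those infusions with at least one IRR.
3. Both shown by window and by schedule (qw or qow) at that infusion.
4. The number of subjects with any IRR, kept as a second line.

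Show pre-treatment status at each IRR descriptively, in the listing or as a simple split, where it can be derived from concomitant medication records. State that it is confounded by indication, because pre-treatment follows a reaction. Protocol 4.5 describes recording the type, amount, duration and reason for a medication but no flag per infusion, so the derivation may be incomplete.

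The cost is SAP wording and some reprogramming; infusions and reactions are already recorded. With about 10 subjects some cells will be sparse, so counts should stand beside every percentage. No dosing or management rule changes.

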10.1.1 Serious Adverse Events

A summary of numbers of events and incidence rates (frequencies and percentages of subjects) of SAEs by SOC and Preferred Term will be prepared for the FAS. No inferential statistical tests will be performed. SAEs will also be tabulated by severity and relationship to SBC-102.

A data listing of SAEs will also be provided, displaying details of the event(s) captured on the CRF.

10.1.2 Dosing and Exposure

All dosing information will be presented in a listing.

The number of weeks in the study and number of study infusions received by subjects will be summarized. The total number of infusions attempted, the number of infusions

completed both without and with a rate change or infusion interruption and the number of infusions where the entire infusion volume was not administered will be presented.

A listing will be provided that summarizes SBC-102 exposure by subject, and date of first and last dose and total number of doses (by dose level) of SBC-102.

10.1.3 Prior and Concomitant medication data

Concomitant medications and treatments are defined as any medication or treatment taken after first dosing with SBC-102 and up to 30 days after last dose with SBC-102. Any prior or concomitant medication(s), treatment(s), and therapy(ies) data will be coded using the WHO-DRUG dictionary. All data will be listed, and the percentages of subjects receiving each coded concomitant medication/treatment will be tabulated.

10.2 Safety Laboratory Evaluations

In general, laboratory evaluations will be displayed in SI units. For some labs (e.g., plasma lipids and serum ferritin), labs will also be displayed in conventional units.

Observed measurements, changes, and percentage changes from baseline to each study timepoint in safety laboratory data will be summarized and listed. Clinically significant abnormal values will be listed separately. Frequencies of abnormal values relative to the laboratory normal range and clinically significant abnormal values will be tabulated for each study timepoint. Shift tables may also be provided.

Spaghetti plots for actual, change from baseline, and percent change from baseline will be created for the following parameters: ALT, AST, GGT, total bilirubin, direct bilirubin, indirect bilirubin, albumin, alkaline phosphatase, total cholesterol, LDL-C, HDL-C, triglycerides, hemoglobin, platelets, PT, PTT, and serum ferritin.

IgG antibody titer values will be tabulated at each assessment time point using summary statistics appropriate to the data. The percentage of subjects who seroconvert, the time to seroconversion, the median and peak IgG antibody titer, the time to peak IgG antibody titer, and the percentage of subjects who tolerize will also be summarized. A further characterization of ADAs, including neutralizing ADAs, may be performed as a separate pooled analysis across studies, and will be reported separately.

10.3 Vital Signs

Within each visit (infusion), descriptive summaries of maximum result and maximum change from the pre-infusion assessment will be summarized.

Baseline will be defined as the non-missing assessment attained before and closest to the date/time of first dose of SBC-102.

A listing of all vital signs data will also be prepared by subject.

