5.1.9 Vital Signs

Vital signs will include pulse rate, respiratory rate, systolic and diastolic blood pressure and core body temperature (rectal or oral). Assessment of pulse rate and blood pressure will be taken after the subject has been in a supine position.

Vital signs will be measured at the timepoints specified in Appendix A. On dosing days, vital signs will initially be recorded pre-infusion, every 15 (\pm 5) minutes during infusion and every 30 (\pm 10) minutes from 0 to 4 hours after completion of the infusion. Once a subject has received a stable dose for at least 2 months, with no moderate-to-severe IARs, vital signs will be recorded pre-infusion and every 30 (\pm 10) minutes during infusion and from 0 to 4 hours after completion of the infusion. After a subject has successfully completed at least 1 year of treatment with no occurrence of moderate-to-severe IARs, the post-infusion period for vital sign monitoring may be shortened from 4 hours to 2 hours.

Page 39 of 76

Additional readings may be taken at the discretion of the Investigator and in the event of an IAR.

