6.4.2 Administration of IMP

Sebelipase alfa should not be infused with other products in the same infusion tubing, as the compatibility in solution with other products has not been evaluated. IMP infusions will be administered at an infusion rate depending on the subject's weight, and must be administered under close supervision of the Investigator, or designee. Sebelipase alfa should not be administered at an infusion rate exceeding 4 ml/kg/hr. For detailed administration instructions please refer to the IMP manual.

Subjects who are medically stable, as determined by the Investigator, may transfer to a local medical center for long-term treatment, contingent upon the local medical center being appropriately qualified and securing the required regulatory and IRB/IEC approvals. Scheduled

study assessments may also be performed at a local medical center with access to the appropriate facilities and expertise.

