10.1 Adverse Events

This SAP specifies standard tabular summaries for adverse events. If the number of any particular type of event is small, the data may be presented in listing format, rather than as a tabular summary.

All AEs will be coded using the MedDRA for the study (version 9.1 or higher).

The severity of AEs will be graded on a 5 point scale according to National Cancer Institute (NCI) Common Terminology Criteria for Adverse Events (CTCAE), version 4.0 or higher.

For the purpose of this study, an IRR will be defined as any AE that occurs during the 2-hour IMP infusion or within 4 hours after the IMP infusion and is assessed by the Investigator as at least possibly related to IMP.

TEAEs are defined as AEs occurring or worsening with an onset at the time of or following the start of treatment with study medication and up to 30 days after the last dose of SBC-102 (completion of the follow-up visit).

Attempts will be made to resolve any missing or partial AE dates with the site; however, if these cannot be resolved, to handle the missing or partial AE start/end date, the following rules will be implemented:

If the start date and time of an AE are partially or completely missing, the AE will be assumed to be treatment-emergent if it cannot be definitely shown that the AE did not occur or worsen during the treatment emergent period (worst case approach). Missing dates and times will not be imputed, but will be shown on listings as incomplete.

Thus, the following approach will be taken:

- If the start time of an AE is missing, but the start date is complete, an AE will only be excluded from treatment-emergent AEs if the start day is before day of first treatment or the start day is after end day of the treatment-emergent period.
- If the start time and day are missing but the start month is complete, an AE will only be excluded from treatment emergent AEs if the start month is before month of first treatment or the start month is after end month of treatment-emergent period or if the stop date/time is before the start of first treatment.
- If the start day and month are missing but the start year is complete, an AE will only be excluded from treatment-emergent AEs if the start year is before year of first treatment or if the start year is after end year of treatment-emergent period or if the stop date/time is before the start of first treatment.

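### SAP 10.3 tabulates only per-infusion vital-sign maxima, while the protocol reduces the number of readings as treatment continues, so maxima from different stages are not comparable

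*SAP*

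**What the plan says.** **The summary.** SAP 10.3 states: "Within each visit (infusion), descriptive summaries of maximum result and maximum change from the pre-infusion assessment will be summarized". Apart from a listing of all vital-sign data, it plans no other vital-sign output. SAP 7.1.1 has data analysed as collected, without imputation. Nothing limits the maximum to a common set of readings or reports how many readings went into it.

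**The readings.** Protocol 5.1.9 sets three stages:
- Stage 1: "vital signs will initially be recorded pre-infusion, every 15" minutes during infusion, then every 30 "minutes from 0 to 4 hours after completion of the infusion".
- Stage 2: "Once a subject has received a stable dose for at least 2 months, with no moderate-to-severe IARs", readings are every 30 minutes during the infusion and for 4 hours after it.
- Stage 3: after at least 1 year of treatment without moderate-to-severe IARs, "the post-infusion period for vital sign monitoring may be shortened from 4 hours to 2 hours".

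Stage 2 is what will happen to a qualifying child. Stage 3 is permitted, not required. Extra readings may be taken at the investigator's discretion or in the event of an IAR.

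**The protocol's own analysis.** Protocol 8.8.3, like the synopsis, plans to summarise the change from the pre-infusion value at every time point during and after infusion. SAP section 13, which lists departures from the protocol's analyses, names only the Denver II total score.

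**The concern.** A maximum depends on how many values it is taken over. On nominal times, the Stage 2 readings are a subset of Stage 1 and the Stage 3 readings a subset of Stage 2. For the same underlying course of a vital sign, the maximum over the subset can never be larger and is smaller on average. That holds for any distribution. A by-visit table of maxima therefore drifts downward as children move to sparser schedules, even if the infusion does exactly what it did before.

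The change of stage is not random. A child with a moderate-to-severe IAR does not qualify for sparser monitoring and keeps the denser schedule. At later visits, children with and without earlier reactions then contribute maxima over different numbers of readings to the same row.

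Changes in vital signs during and after infusion are a named safety endpoint (Protocol 3.2.2.2, SAP 2.3). There is no control arm and only about 10 children, so nothing else in the table would expose the artefact. A reader comparing early with late visits could take part of the reading schedule for better tolerability.

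**Working it through.** The documents give no reading count, no expected maximum and no SD for vital signs, so there is no plan figure to reproduce. Results are in units of the within-infusion SD.

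**Inputs**
- Intervals and monitoring periods: Protocol 5.1.9, as above.
- Infusion length: 2 hours, which appears only in the SAP 10.1 definition of an infusion-related reaction ("any AE that occurs during the 2-hour IMP infusion or within 4 hours after the IMP infusion"). Protocol 6.4.2 fixes no length ("IMP infusions will be administered at an infusion rate depending on the subject's weight"), so 1 to 4 hours was also tried.

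**Step 1: readings after the start of a 2-hour infusion**

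n = infusion minutes / interval + post-infusion minutes / 30
- Stage 1: 120/15 + 240/30 = 8 + 8 = 16
- Stage 2: 120/30 + 240/30 = 4 + 8 = 12
- Stage 3: 120/30 + 120/30 = 4 + 4 = 8

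Counting a reading at the moment the infusion ends gives 17, 13 and 9.

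**Step 2: expected maximum with no drug effect**

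For n independent standard normal readings, E[max] = ∫ x·n·φ(x)·Φ(x)^(n−1) dx. The autocorrelated rows are simulated. The pre-infusion value has mean zero here, so subtracting it leaves the expected maximum change equal to the expected maximum.

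| Readings | 16 | 12 | 8 | Fall 16→12 | Fall 16→8 |
|---|---|---|---|---|---|
| Independent | 1.77 | 1.63 | 1.42 | 7.8% | 19.4% (0.34 SD) |
| Autocorrelated, 60-min decay | 1.46 | 1.39 | 1.15 | 5.1% | 21% (0.31 SD) |
| Correlation 0.9 at 15 min | 1.17 | 1.11 | 0.89 | 4.9% | 24% (0.28 SD) |

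**Step 3: other infusion lengths, independent readings**

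| Length | Readings by stage | E[max] by stage | Fall, first to last |
|---|---|---|---|
| 1 h | 12, 10, 6 | 1.63, 1.54, 1.27 | 0.36 SD |
| 3 h | 20, 14, 10 | 1.87, 1.70, 1.54 | 0.33 SD |
| 4 h | 24, 16, 12 | 1.95, 1.77, 1.63 | 0.32 SD |

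**Step 4: a constant drug effect peaking at the end of a 2-hour infusion**

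| Effect | Correlation at 15 min | 16 | 12 | 8 | Fall 16→8 |
|---|---|---|---|---|---|
| 1 SD | 0 | 2.138 | 1.963 | 1.865 | 0.273 SD (12.8%) |
| 2 SD | 0 | 2.772 | 2.548 | 2.519 | 0.253 SD (9.1%) |
| 1 SD | 0.9 | 1.508 | 1.450 | 1.325 | 0.183 SD (12.1%) |
| 2 SD | 0.9 | 2.186 | 2.125 | 2.086 | 0.100 SD (4.6%) |

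A real effect pulls the maximum towards the end of infusion, which every stage measures, so the artefact is smaller but still present.

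**Step 5: restricting to common readings**

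The readings shared by all stages are every 30 minutes during infusion and to 2 hours after it: 4 + 4 = 8. With independent readings and no drug effect, the expected maximum is then 1.42 SD in every stage.

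**The case against.** The strongest case against this is that it is a small matter in a descriptive table. No formal hypothesis tests are planned, and SAP 10.3 announces no comparison across visits. Tolerability over time is also addressed by adverse-event and reaction frequencies by treatment period, and every reading is listed. With about 10 children, the standard error of a by-visit mean maximum change is about 0.33-0.37 SD, so the whole three-stage artefact is roughly one standard error at any single visit. All of this stands and limits the weight of the point. It does not remove it: the artefact runs in one direction and can accumulate as a trend across many visits, and nothing in the table would warn the reader.

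Some stronger readings are tempting, and the documents do not support them:
- **The full 20% fall will occur.** Only the first step is scheduled. The cut to 2 hours may be used or not, child by child.
- **Maxima are confounded with dose.** The first step needs a stable dose, but Protocol 5.1.9 does not say that 15-minute readings resume after a later dose increase. Confounding with dose is possible, not established.
- **Outlying readings fall by about 40%.** Under no drug effect, the chance of any reading above 2 SD does fall from 31% to 24% to 17% (independent) or from 21% to 13% (60-minute autocorrelation), a drop of about 38-45%. SAP 10.3 plans no such proportion.

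A further objection concerns the remedy. Replacing the tabulated maximum with one over common readings would take the 15-minute readings, those from 2 to 4 hours after infusion and any IAR-triggered readings out of a safety table. These last are the readings most likely to catch a real excursion. That objection is right, and the fix below adds a summary instead of replacing one.

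**Conclusion.** The point holds as a modest, one-directional bias in a secondary safety summary. With no drug effect, the expected maximum falls by about 5-8% at the scheduled step and by about 20% if the optional step is also used, or about 0.3 SD. With a constant effect of 1 to 2 SD peaking at the end of infusion, the total fall is 0.10-0.27 SD. It was present in every scenario tried.

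The counts of 16, 12 and 8 rest on the 2-hour infusion named only in SAP 10.1; the total fall persists for 1 to 4 hours. The sizes assume normal readings at nominal times and no unscheduled readings. The direction needs no distributional assumption. Raw maxima may also drift as children grow, so the artefact is clearest in the maximum change from pre-infusion. The primary endpoint is unaffected.

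The protocol's planned per-time-point change would not have this problem, and SAP section 13 does not record that it was dropped. One caution applies: the SAP is written to protocol Amendment 10 of 24 January 2014, while the protocol in hand carries a January 2016 date. The wording of 5.1.9 and 8.8.3 in Amendment 10 cannot be checked here.

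**What to change.** In SAP 10.3:
1. Keep the all-readings maximum result and maximum change in the table, and show the number of readings behind them at each visit.
2. Add beside them one like-for-like summary. This is either the change from pre-infusion at each nominal time point, as Protocol 8.8.3 plans, or the maximum over the readings common to all monitoring stages (nominal 30-minute readings during infusion and to 2 hours after it).
3. State that change over time will be described only from the like-for-like summary.

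If the per-time-point summary is not restored, record the departure in SAP section 13.

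The cost is some extra table rows and a programming filter on nominal time. It needs no new data and no change to monitoring, and no reading leaves the safety table.
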